
 Rate of decline in eGFR (eGFR slope) will be summarized using mean, standard deviation, minimum, P25, median, P75, and maximum by treatment group. Summaries using on-and off-treatment eGFR, on-treatment eGFR only, and on-treatment eGFR only with subjects who had baseline eGFR $\geq 15\text{ml/min/1.73m}^2$ will be produced. For the MMRM analyses of change from baseline in eGFR to Week 52, an LSMEANS statement will provide adjusted treatment group means and standard errors and a point estimate and two-sided 95% confidence interval for the adjusted mean treatment difference (daprodustat – darbepoetin alfa) and a one-sided superiority p-value for this test. Summaries using on-and off- treatment eGFR, on-treatment eGFR only, and on-treatment eGFR only with subjects who had baseline eGFR $\geq 15\text{ml/min/1.73m}^2$ will be produced. For the analysis of eGFR slope, the adjusted treatment group means of slope and standard errors, a point estimate and two-sided 95% confidence interval for the adjusted mean treatment difference (daprodustat – darbepoetin alfa) will be produced. The one-sided superiority p-value for this test will be calculated. Summaries using on-and off- treatment eGFR, on-treatment eGFR only, and on-treatment eGFR only with subjects who had baseline eGFR $\geq 15\text{ml/min/1.73m}^2$ will be produced. A line plot showing change from baseline over time for eGFR treatment group will be produced using on-and off- treatment eGFR, on-treatment eGFR only, and on-treatment eGFR only with subjects who had baseline eGFR $\geq 15\text{ml/min/1.73m}^2$. 	
Model Results Interpretation	

 One-sided p-values will be compared to 0.025 to assess nominal significance. 	
Subgroup Analysis	

 Summaries and analyses for eGFR and eGFR slope will also be performed for the subgroups of ADPKD and non-ADPKD subjects using on and off treatment eGFR values. P-values will not be produced for the treatment comparisons within the subgroups. 	

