
 • A summary of the number and percentage of subjects having first-occurrence MACE will be provided by treatment group. The number and percentage of the types of events that make up the first occurrence of MACE will also be provided by treatment group. • A summary of all MACE including the number and percentage of subjects and number of events (including first and subsequent MACE) by type of event will be provided by treatment group. Subjects experiencing MACE will be further broken down into subjects who experienced exactly one MACE, subjects who experienced exactly two MACE, and subjects who experienced more than two MACE. The number and percentage of subjects in each of these categories by event type combinations will be provided by treatment group. • The hazard ratio, two-sided 95% CI, one-sided p-value for the statistical non-inferiority test, and one-sided p-value for the superiority test will be presented for the comparison of daprodustat vs. darbepoetin alfa using the Cox Proportional Hazards model. The number and percentage of subjects with a MACE event and the number censored at the end of the study, the MACE incidence rate per 100 person-years, and the absolute rate difference per 100 person-years and associated two-sided 95% CI will be displayed with the results of the Cox proportional hazards regression model. • To inform on the validity of the adjusted Cox proportional hazards model, the proportional hazards assumption will be assessed by plotting the logarithm of the negative logarithm of the estimated survivor function against the logarithm of time, for each treatment group. If the hazards are proportional, the lines should be approximately parallel. • The hazard ratio, two-sided 95% CIs and one-sided non-inferiority and superiority p-values will be displayed on a forest plot together with supportive analysis results (i.e., excluding the Tipping Point Analysis).

CV Safety (MACE) Co-Primary Statistical Analyses

 Time from Randomization to first adjudicated MACE event or end of trial will be evaluated using Kaplan-Meier (KM) methodology and displayed graphically for the comparison of daprodustat vs. darbepoetin alfa. A listing of all MACE events occurring during the study will be provided and will include treatment, site ID, unique subject ID, select demographic information, event type, event date, and study day.
Model Results Interpretation

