
 CKD progression is defined as (see Section 10.6.4): 
 40% decline in eGFR from baseline (confirmed 4 – 13 weeks later) or; End stage renal disease (ESRD) as defined by either: 
 Initiating chronic dialysis for ≥ 90 days*, or Not initiating chronic dialysis when dialysis is indicated (adjudicated), or Kidney transplantation 
*Adjudicate only if the duration of dialysis is <90 days.
 For purposes of summary and analysis, the components of CKD progression include: 
 Confirmed 40% eGFR decline Chronic dialysis. The chronic dialysis component includes subjects who initiate chronic dialysis for ≥ 90 days (non-adjudicated), positively adjudicated cases of dialysis less than 90 days with expected chronicity, and positively adjudicated cases where dialysis was indicated for a chronic condition but not provided. Kidney transplant Summaries and Analysis of CKD progression and its components will be restricted to the subset of subjects with baseline eGFR ≥ 15 ml/min/1.73m². Due to the presence of all-cause mortality as a competing risk, analysis of time to progression of CKD will be performed using Fine and Gray's subdistribution hazards analysis model, adjusting for the same factors as the co-primary MACE analysis (Section 7.2.2) for the evaluation of superiority. 
 For supportive purposes, the Cox Proportional Hazards model used in the co-primary MACE analysis will also be run. Analysis will include only the CKD progression events occurring within the time period for follow-up of CV endpoints as described in Section 10.6.4. For the components of CKD progression intended to go through the adjudication process, only the adjudicated results will be used.
Model Results Presentation

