
 • Analysis of the endpoints above (except the recurrent event analysis and components of progression of CKD) will be performed individually using an analysis model identical to that described for the co-primary MACE analysis for the evaluation of superiority, using the event dates defined in Section 10.6.4. Additionally, supportive summaries and analyses for the following endpoints will be generated including fatal events which are identified only through the death endpoint page and do not have a corresponding positively adjudicated endpoint event (see Section 10.6.4): 
 ○ MI ○ Stroke ○ Thromboembolic events: Pulmonary Embolism • For purposes of time-to-event models, subjects who have never been hospitalized will be right-censored (i.e., are still considered to be at-risk) for an all-cause hospital re-admission within 30 days. • The recurrent event analysis of MACE or hospitalization for HF events will use the Prentice, Williams, Peterson (PWP) model [Prentice, 1981], based on the Cox proportional hazards model, to analyze the multiple event data. This model analyzes the time to first, second, etc. events while accounting for the correlation of events within an individual subject. Subjects are at risk for a k^{th} event only if they survived a $(k-1)^{\text{st}}$ event. For the models described below, if there are not at least 15 k^{th} events per arm, the treatment effect associated with the k^{th}, $(k+1)^{\text{th}}$, etc. events will not be estimated. All event times will be relative to randomization, as opposed to intra-event time (i.e. total times rather than gap times will be used). 
Three models will be used. The first model will estimate a common treatment effect, regardless of the number of events experienced by subjects. A second model will be run that allows the treatment effects to differ depending on the number of events experienced by subjects. A third model will be run that allows the treatment effect associated with the time to 1st MACE or hospitalization for HF to differ from a common treatment effect estimated for time to 2nd, 3rd, 4th, etc. MACE or hospitalization for HF. The common treatment effect associated with the time to 2nd, 3rd, 4th, etc. in the third model would provide support for a treatment effect on time to subsequent MACE or hospitalization for HF.
 
It is possible for a patient to die in conjunction with experiencing a series of events in a short

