
imaging, other), and treatment (thrombolytic therapy, thrombectomy, angioplasty, stent, surgical intervention, not specified).
 
 • The model results presentation for the endpoints above (except the recurrent event analysis) will be identical to the co-primary MACE model results, with the single exception being the one-sided p-value presented will be for the test of superiority of daprodustat vs. darbepoetin alfa. • For the recurrent events analysis, hazard ratios, two-sided 95% CIs and one-sided chi-squared p-values associated with treatment effects (daprodustat vs. darbepoetin alfa) will be presented for the three models described above. • Summaries that partition the investigator-reported events as (adjudicated to the same event, adjudicated to a different event, adjudicated as a non-event) will be presented. Summaries of investigator/adjudicator agreement by type of event reported by investigators may also be reported. • A summary of all-cause hospitalization will be provided by treatment group including summaries of the number of hospitalizations per subject, average length of stay per hospitalization and primary diagnosis at discharge by system organ class and lower level term. • A summary of all-cause hospital re-admission within 30 days will be provided by treatment group including summaries of the number of re-admissions within 30 days per subject and the primary diagnosis at re-admission discharge by system organ class and lower level term. • A listing of all all-cause mortality events that occur during the study will be provided. This listing will include treatment, site ID, unique subject ID, select demographic information, event date, study day, and cause of death.
Model Results Interpretation

 • One-sided p-values will be compared to 0.025 to assess nominal significance.

Blood Pressure

Secondary Safety Statistical Analyses: Blood Pressure
Endpoint(s)

 • Change from baseline in SBP, DBP and MAP at Week 52 and at end of treatment • Number of BP exacerbation events per 100 patient years • N (%) of subjects with at least one BP exacerbation event during study
Model Specification

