
 • Date of withdrawal for subjects withdrawing (i.e., subjects who actively withdraw or are deemed lost to follow-up) from study or date of completion of study for subjects who complete the study. If the date of study withdrawal entered in the eCRF is before the last study contact date, the last study contact date will be used as the study withdrawal date for analysis. 
 • Note: Subjects who die while on study are considered as having completed the study • The eCRF allows for the possibility of missing or partial dates to be recorded for the study completion/withdrawal date on the Study Conclusion form (i.e., missing day, or day and month, or day and month and year). In such a case, or in case of subjects who are missing a Study Conclusion form, the following conventions will be applied in order to impute a study completion/withdrawal date: 
 • Missing day: 
 ▪ The last day of the month will be used, unless the last study contact date also occurs in the same month; in the case, the last study contact date will be used. • Missing day and month: 
 ▪ '31' will be used for the day and 'Dec' will be used for the month, unless the last study contact date also occurs in the same year; in this case, the last study contact date will be used. • Missing day, month and year: 
 ▪ The last study contact date will be used. • If both death and study completion/withdrawal have missing or partial dates, they will be imputed as specified (see Section 10.6.1 and Section 10.6.4). If the imputed death date is prior to the imputed study completion/withdrawal date, then the study completion/withdrawal date will use the imputed death date instead.
Planned/Actual Visit Dates

 • Planned/actual visit dates will be defined as follows: 
 ○ Week 28 date: Non-missing Week 28 visit start date (from SV domain), otherwise randomization date + 28*7 ○ Week 36 date: Non-missing Week 36 visit end date (from SV domain), otherwise randomization date + 36*7 ○ Week 52 date: Non-missing Week 52 visit end date (from SV domain), otherwise randomization date + 52*7 ○ End of Study date: Non-missing End of Study visit start date (from SV domain), otherwise the middle of the End of Study window.
Stabilization Period

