
The period for capturing CV safety endpoints begins at randomization. The end of this time period is the date of study completion/withdrawal, with the exception that if a death has been reported in the clinical database after this time, then the death will be included in the analysis.
 
Any endpoints that occurred before the start of this time period are considered to be prior to the time period for follow-up of cardiovascular safety events, and any endpoints that occurred after the end of this time period are considered to be post the time period for follow-up of cardiovascular safety endpoints.

Time Period for Vital Status

The period for capturing vital status begins at the date of randomization. The end of this time period is defined as follows:
 
 • For all subjects known to have died, use the date of death • For all subjects who complete the study, use the study completion date (see Section 10.6.1) • For all subjects who withdraw from the study, but vital status has been ascertained, and are known to have not died – use the latest date last known to be alive. If vital status has not been ascertained following study withdrawal, use the study withdrawal date. 
Any endpoints that occurred before the start of this time period are considered to be prior to the time period for vital status, and any endpoints that occurred after the end of this time period are considered to be post the time period for vital status.

Time Period for On-treatment Cardiovascular Endpoints

The period for capturing on-treatment CV safety endpoint events begins at the treatment start date. The end of this time period is defined as follows:
 
 • For subjects whose last non-zero dose date is missing and who took randomized treatment, use date of study withdrawal/completion • For subjects continuing on study past the last non-zero dose date +28 days, use (last non-zero dose date + 28) • For subjects whose study withdrawal/completion date is on or before (last non-zero dose date +28), use date of study withdrawal/completion 
If the censoring date as defined above for on-treatment CV safety endpoints is after the censoring date as defined for the primary analysis during the time period for follow-up of CV safety endpoints,

CV Safety Endpoints

then use the censoring date for the primary analysis time period.

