	
 To inform on the validity of the adjusted Cox proportional hazards model, the proportional hazards assumption will be assessed by plotting the logarithm of the negative logarithm of the estimated survivor function against the logarithm of time, for each treatment group, region and current ESA use at randomization. If the hazards are proportional, the lines should be approximately parallel. Should there be evidence of a violation of the proportional hazards assumption, the following methods may be considered: 
 Use of a stratified Cox proportional hazards model (including prognostic factors in a STRATA statement in PROC PHREG, rather than in the MODEL statement)
Endpoint(s)	
 Time to first event endpoints with death as a competing risk

Analysis	
• Cox proportional hazards

• If there is a notable difference between one or both of all-cause mortality and non-CV mortality, and one or more of the secondary CV endpoints that do not include death as a component, then additional analysis methods to address competing risks may be pursued such as:
○ Fine & Gray's Subdistribution Hazards [Fine, 1999]○ Use of cumulative incidence functions instead of KM curves	

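### Kaplan-Meier figures for the secondary CV endpoints without all-cause death censor competing deaths and so overstate the plotted event probability

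*SAP*

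**What the plan says.** - **Model.** SAP 8.2.2.2 says the additional secondary CV endpoints, other than the recurrent-event analysis and the CKD components, "will be performed individually using an analysis model identical to that described for the co-primary MACE analysis for the evaluation of superiority".
- **Presentation.** The same section adds: "The model results presentation for the endpoints above (except the recurrent event analysis) will be identical to the co-primary MACE model results". The one further exception is that the p-value is for superiority. Under 7.2.2 the MACE presentation comprises counts and percentages, the Cox hazard ratio, the rate per 100 person-years, the rate difference, and a curve: "Time from Randomization to first adjudicated MACE event or end of trial will be evaluated using Kaplan-Meier (KM) methodology". Table 8 in 8.2.2.1 marks a figure from the statistical analysis for each of the endpoints at issue.
- **What happens at death.** Section 10.6.4.1, on the follow-up period for CV endpoints: "The end of this time period is the date of study completion/withdrawal". Section 10.6.1: "Subjects who die while on study are considered as having completed the study".
- **Competing-risk provision.** Section 10.12.1 names time-to-first-event endpoints with death as a competing risk and assigns them Cox. If mortality and one of these endpoints differ noticeably, "then additional analysis methods to address competing risks may be pursued such as" Fine and Gray, and cumulative incidence functions in place of Kaplan-Meier curves. It gives no threshold.
- **Contrast.** For CKD progression, 8.2.1.2 fixes Fine and Gray in advance, "Due to the presence of all-cause mortality as a competing risk", with cumulative incidence plots as the main figure and Kaplan-Meier as support. Section 8.2.2.2 assigns the individual CKD components that same model.

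**The concern.** Kaplan-Meier is right for MACE because every death is an event. Copied to an endpoint without all-cause death, it treats a patient who has died as someone who could still have the event later. The complement of the curve then estimates a probability in a world without competing death, which is higher than the proportion of patients who will have the event.

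The condition in 10.12.1 does not cure this. The overstatement depends on the level of the death rate, not on whether mortality and the endpoint show different results, and the condition can be judged only once results are available. The plan has already accepted the argument for CKD progression. In a cardiovascular safety trial, readers will take absolute risks from these figures.

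There is also a drafting mismatch. The model paragraph of 8.2.2.2 sets aside both the recurrent-event analysis and the CKD components, but the presentation sentence sets aside only the former. As worded, components modelled by Fine and Gray receive the MACE Cox and Kaplan-Meier presentation.

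**Working it through.** **Step 1: are deaths censored?** The SAP does not say so in one sentence; it follows from two rules. CV follow-up ends at study completion or withdrawal (10.6.4.1), and a death on study counts as completion (10.6.1). A death that is not itself the event therefore ends follow-up without an event.

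**Step 2: which endpoints?** MI, stroke, heart-failure hospitalization, thromboembolic events, all-cause hospitalization and 30-day re-admission; also CV mortality and CV mortality or non-fatal MI, through non-CV death. All-cause mortality and the composites containing MACE are not affected. Under 10.6.4.1, a fatal MI, stroke or pulmonary embolism with a positively adjudicated event does count, so for those endpoints the competing death rate is below the all-cause rate.

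**Step 3: size.** The SAP gives no event probability or death rate for these endpoints, so there is no figure to reproduce and the rates below are assumptions. With constant event hazard λ and competing-death hazard μ:

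- death censored: 1 − KM = 1 − exp(−λt)
- cumulative incidence: CIF = λ/(λ+μ) × [1 − exp(−(λ+μ)t)]

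For λ = 0.04, μ = 0.045, t = 3: 1 − exp(−0.12) = 11.31%, and 0.04/0.085 × [1 − exp(−0.255)] = 10.59%.

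| Events per 100 PY | Deaths per 100 PY | Years | 1 − KM | CIF | Gap (points) |
|---|---|---|---|---|---|
| 4 | 4.5 | 3 | 11.31% | 10.59% | 0.72 |
| 4 | 4.5 | 4 (about Week 208) | 14.79% | 13.56% | 1.22 |
| 1 | 6 | 4 | 3.92% | 3.49% | 0.43 |
| 3 | 6 | 2 | 5.82% | 5.49% | 0.33 |
| 3 | 6 | 4 | 11.31% | 10.08% | 1.23 |
| 5 | 6 | 4 | 18.13% | 16.18% | 1.95 |
| 30 (hospitalization) | 6 | 2 | 45.12% | 42.77% | 2.35 |
| 30 (hospitalization) | 6 | 4 | 69.88% | 63.59% | 6.29 |

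For 1 to 5 events and 3 to 6 deaths per 100 person-years, the relative overstatement is 3% to 6% at 2 years and 6% to 12% at 4 years. At 10 deaths per 100 person-years it reaches 10% and 21%.

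**Step 4: which death rates are plausible?** The SAP targets 664 first MACE and shows N = 4500, so 664/4500 = 14.8% of subjects. With mean follow-up assumed at 1.9 to 2.5 years, that is 664/(4500 × 2.5) = 5.9 to 664/(4500 × 1.9) = 7.8 first MACE per 100 person-years, deaths included. A death rate of 4.5 fits. A rate of 10 would need mean follow-up near 664/(4500 × 0.10) = 1.5 years even if every first MACE were a death, so those upper values are an outer bound.

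**Step 5: simulation check.** With 400,000 simulated subjects, λ = 0.03, μ = 0.06 and 4 years, 1 − KM was 11.35% and the true proportion 10.12%, matching the formulas. The simulated rate was 3.01 per 100 person-years against a true 3, so censoring deaths does not inflate the person-year rate.

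**Step 6: between-arm effect.** Raise deaths by 10% in one arm (μ = 0.0495). Its 3-year CIF becomes 0.04/0.0895 × [1 − exp(−0.2685)] = 10.52%, against 10.59%. Kaplan-Meier shows 11.31% in both arms and so hides 0.07 points. The standard error per arm of 2250, ignoring censoring, is √(0.1059 × 0.8941/2250) = 0.65 points, and for the difference 0.65 × √2 = 0.92. The hidden difference is therefore about 0.08 standard errors.

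**The case against.** The strongest reply is that these endpoints exist to compare arms and that nothing used for the comparison is wrong. Censoring deaths in a Cox model gives a valid cause-specific hazard ratio. The percentages, person-year rates and rate differences are not inflated, and 7.2.2 plans Kaplan-Meier as a graph, with no tabulated Kaplan-Meier risk. Step 6 shows that the between-arm distortion is negligible unless mortality differs materially, which is roughly the situation 10.12.1 has in mind. The endpoints are nominal, and the more important composites already include all-cause death. All of this stands.

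It follows that three stronger readings fail. A reader might infer that the hazard ratios or p-values are biased; they are not. A reader might infer that all the reported absolute risks are too high; only the curve is. A reader might infer that the method behind the main result is chosen after unblinding; the Cox model is fixed in 8.2.2.2, and the open choice concerns the curve and additional analyses. Nor does fixing Fine and Gray for CKD progression, a multiplicity-controlled endpoint, oblige the sponsor to report it for every nominal endpoint. The cumulative incidence plots for adverse events of special interest in 8.2.4.2 are weak precedent, since they are themselves optional.

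What the reply does not answer is that the planned figure shows the wrong quantity, for a reason the plan itself accepts for CKD progression.

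**Conclusion.** The point holds for the figures only. For the endpoints in Step 2, the planned Kaplan-Meier curve, read as a probability, is too high whenever competing deaths occur. At 4 events and 4.5 deaths per 100 person-years the excess is about 0.7 points at 3 years and 1.2 at 4 years. At 1 event per 100 person-years it is under half a point at 4 years with 6 deaths per 100 person-years. For all-cause hospitalization it could be several points, though less if death before a first hospitalization is uncommon. These sizes rest on assumed constant rates; the direction does not depend on them. The co-primary and principal secondary conclusions are untouched. The mismatch over presentation of the CKD components is a separate wording error that needs correcting whatever the size of the bias.

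**What to change.** 1. In SAP 8.2.2.2, for the endpoints in Step 2, make cumulative incidence curves the planned figure, with any death not counted as an event as the competing event. Kaplan-Meier can remain at most as support, as for CKD progression. Keep the Cox hazard ratio.
2. In 10.12.1, remove the results-based condition for the choice of curve. Fine and Gray for these nominal endpoints can stay optional or supportive.
3. In the presentation sentence of 8.2.2.2, also except the CKD progression components and refer them to the CKD progression presentation in 8.2.1.2.

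The cost is a few lines of text and a change of plotting method to one already planned for CKD progression. No further data are needed. The plotted curves will be slightly lower, and no test or tabulated estimate for the CV endpoints changes.
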